### **2.3.1 Patient disposition**

Patient disposition was summarized for all patients by absolute and relative frequencies of patients completing the study phases screening, randomization, treatment and study completion. Reasons for discontinuation of screening, treatment and study were shown by

treatment for all patients (screening) resp. the Randomized Set (treatment and study). The number of patients per analysis set was summarized by treatment.

Protocol violations were reported descriptively by treatment and a listing was generated for each treatment for all screened patients.

## **2.4 Treatments (study treatment, rescue medication, concomitant therapies, compliance)**

### **2.4.1 Study treatment / compliance**

Duration (days) of Everolimus application were summarized. Dose interruptions, i.e. days with dose of 0 mg were considered for calculation of duration. Daily Everolimus dose levels were summarized with mean, standard deviation, minimum, median, and maximum by visit. Dosage averages were calculated including and excluding zero doses for periods of temporary interruption of study medication regardless of whether this was due to safety reasons or patients' non-compliance. Assignment of the DAR records to the visits were calculated based on the visit dates. Reasons for dose adjustments (including temporary dose interruption) were presented by frequency distribution. These frequencies of dose reduction (including temporary dose interruption) for safety reasons as per protocol guidelines were presented by study period. Permanent treatment discontinuations were analyzed by frequencies.

These analyses were performed per treatment group, for the SAF population and related to the study periods in the randomized treatment period (see section 2.1 Data analysis general information). For the run-in period, duration and mean daily dose were summarized for the ENR population displaying both, randomized versus not randomized patients as well as the initial treatment groups CNI+MPA versus CNI+ Everolimus

Daily Cyclosporin A and Tacrolimus doses adjusted by the patients' visit-specific body weight and MPA doses were summarized by visit and in the same way as Everolimus. Data were presented separately for each treatment group. Induction therapy (Basiliximab or ATG or no induction) received by patient was summarized by treatment group, for the SAF population. The distribution of the specific CNI medications was summarized by treatment group.

Duration (days) of treatment with Cyclosporin A, Tacrolimus, MPA, and steroids as well as frequency of Cyclosporin A, Tacrolimus and MPA dose adjustments (including temporary dose interruption) for safety reasons as per protocol guidelines were determined. Reasons for dose adjustments (including temporary dose interruption) were presented by frequency distribution. Permanent treatment discontinuations were analyzed using frequency distribution. All other immunosuppressive therapies were summarized by ATC (Anatomical, Therapeutic, Chemical) classes.

All analyses were presented per treatment group and study period (see 2.1 Data analysis general information).

## **2.4.2 Prior, concomitant and post therapies**

Medications other than those mentioned in section 2.4.1 taken concomitantly with the study medication were summarized by treatment group and study period through frequency tables. Concomitant medication was coded and summarized according to the ATC classification system.

## **2.5 Analysis of the primary objective**

### **2.5.1 Primary endpoint**

The primary aim of this study was to show superior renal function under the CNI-free regimen compared to the CNI-based regimen with respect to GFR as calculated by MDRD method (cGFR/MDRD).

The primary variable for assessment of renal function was the

- glomerular filtration rate (GFR) at Month 18, as assessed by the MDRD method (recalculated values, see Appendix, section 5.1.2 Calculated GFR).

### **2.5.2 Statistical hypothesis, model, and method of analysis**

The null hypothesis  $H_0$  of similar GFR level in both treatment groups

$$H_0: \mu_{\text{CNI-free}} = \mu_{\text{CNI-based}}$$

was tested against the two-sided alternative hypothesis of different efficacy (different GFR levels at month 18 after Tx) of the CNI-free regimen compared to the CNI-based regimen

$$H_1: \mu_{\text{CNI-free}} \neq \mu_{\text{CNI-based}}$$

with an analysis of covariance (ANCOVA) using “treatment” and “center” as factors and “baseline GFR value at Baseline visit 2 (Month 6)” as covariate. Type-I error probability was set to a two-sided  $\alpha=0.05$ . Adjusted means (=LS-means, LS: least square means) were presented for the treatment contrast of GFR at Month 18 post Tx together with its confidence interval and a two-sided p-value.

The FAS population was used for the primary analysis. This analysis followed the intention-to-treat principle and thus reflects the actual performance of the investigational drug under practical conditions (“pragmatic approach”).

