- Death / graft loss / re-transplantation / acute rejection associated with hemodynamic compromise / biopsy proven acute rejection of ISHLT 1990 grade \geq 3A resp. ISHLT 2004 grade \geq 2R / treated acute rejection / loss to follow-up as well as treatment failure as a composite endpoint.
- Major Adverse Cardiac Events (MACE)
- Electrocardiogram (ECG)
- Echocardiogram

Safety assessments

- Infections
- (Serious) Adverse Events
- Physical Examination
- Vital Signs
- (Safety) Laboratory evaluation

Pharmakokinetic assessments

- Blood trough levels (C0-h) of Cyclosporin A, Tacrolimus, MPA and Everolimus

Data analysis

Statistical analysis and report writing will be performed when all patients have completed Month 18 after Tx assessment.

Change in glomerular filtration rate (MDRD method) will be used as the primary criterion in order to demonstrate the CNI-free regimen is superior to the CNI-based regimen regarding the prevention of renal failure. Primary analysis will be performed with the ITT population.

Type I error probability is set to 0.05, two-sided.

All other safety and efficacy variables will be presented by descriptive statistics and compared between both treatments using suitably chosen tests for unpaired or paired (laboratory data and vital signs) observations. Categorical variables will be analyzed with the χ^2 -test or Fisher's exact test. Event data will be assessed by Kaplan-Meier statistics and compared between the two groups with the logrank test. In addition to the comparison of the two treatment groups, further comparisons will be made with the group of patients who were not eligible for randomization at Baseline visit 2.

Sample size

The probable difference between the CNI-free - and the CNI-group in the GFR is estimated as $\delta = 8$ ml/min with $\sigma = 16$ ml/min. With $\alpha=.05$ (two sided significance level) and $1-\beta = 90\%$ (power), $n=86$ patients per group are required to demonstrate superior efficacy of the CNI-free regimen compared to the CNI-group in the GFR using the t-test [REDACTED]. To compensate for some uncertainty of the assumptions for sample size calculation, the calculated sample size is increased by $\approx 15\%$. Therefore, a total number of $N=200$ patients ($n=100$ per treatment group) will be randomized and treated in both treatment arms after Baseline visit 2.

1 Background

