The primary objective of this trial is to demonstrate superiority of a CNI-free regimen with respect to the renal function at Month 18 post Tx assessed by glomerular filtration rate – MDRD method – as compared to the standard CNI-based regimen in heart transplant patients.

Secondary objectives of this trial are:

- to assess occurrence of treatment failures up to or at Month 18 post Tx, while treatment failure is defined as a composite endpoint of biopsy proven acute rejection of ISHLT 1990 grade \geq 3A (ISHLT 2004 grade \geq 2R), acute rejection episodes associated with hemodynamic compromise, graft loss / re-transplant, death, loss to follow up (at least one condition must be present)
- to assess incidence of MACE and each of its components at Month 18 post Tx
- to assess renal function by glomerular filtration rate - Cockcroft-Gault method - at Month 12 and 18 post Tx
- to assess renal function (serum creatinine) and evolution of renal function between Month 6 and 18 post Tx (creatinine slope)
- to assess safety and tolerability at Month 6, 9 and 18 post Tx (according to safety parameters specified in [section 7.6](#))

4 Study design

This is a prospective, multi-center, randomized, controlled, parallel group, open label study in heart transplant recipients. A total of 200 patients fulfilling the inclusion and exclusion criteria at Baseline visit (Month 6 post Tx) will be randomized to the two treatment groups. Enrollment will be continued until the required sample size is achieved.

Once consent is obtained, screening data will be collected to determine each patient's eligibility for study participation. Screening assessment will be performed at Month 3 post Tx and relevant data from transplantation will be recorded retrospectively.

During the first three months post Tx the patients may be treated according to center standards. Latest after study inclusion (Month 3 post Tx ± 2 weeks), the patients should receive an immunosuppressive regimen consisting of Cyclosporin A (based on C0-h level) or Tacrolimus (based on C0-h level) + Everolimus (target C0-h level: 5 – 10 ng/mL) or MPA + corticosteroids.

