The study population will consist of 200 de novo heart transplant patients (100 patients per treatment group) who are randomized to the two treatment groups at Baseline visit (Month 6 post Tx). The patients will be recruited from about 10 transplant centers in Germany.

Inclusion / Exclusion criteria for Enrollment (Month 3 post Tx)

The investigator must ensure that all patients who meet the following inclusion criteria and none of the exclusion criteria are offered enrollment in the study. No additional exclusions can be applied by the investigator, in order that the study population will be representative of all eligible patients.

Inclusion Criteria

The following inclusion criteria must be present at enrollment (Month 3 post Tx)

1. Males or females, aged 18 – 70 years
2. Recipients of de novo cardiac transplants, 3 months prior to enrollment
3. Patients with sufficient renal function, i.e. GFR >30 and <100mL/min
4. Patients who are willing and able to participate in the study and from whom written informed consent has been obtained.
5. Women of childbearing potential should have a negative serum or urine pregnancy test within 7 days prior to or at screening. Females are eligible if they are postmenopausal for at least 24 months past last natural menses. Study medication should not be administered until a negative pregnancy test report is obtained. Two or more acceptable methods of contraception should be started 1 month prior to beginning study drug unless abstinence is the chosen method, during therapy, and for 3 months after stopping the study. Abstinence is an allowed contraceptive method if in the judgment of the investigator the patient is reliably abstaining. Acceptable forms of birth control include any two or more of the following methods: surgical sterilization (e.g. bilateral tubal ligation, hysterectomy), hormonal contraception (implantable, patch, oral), IUD and barrier methods (male or female condom with spermicidal gel, diaphragm, sponge, cervical cap). Periodic abstinence (e.g. calendar, ovulation, symptothermal, post-ovulation methods) and withdrawal are not acceptable methods of contraception.

Exclusion Criteria

The following exclusion criteria must not be present at enrollment (Month 3 post Tx)

1. Multi-organ recipients, re-transplantation, or previous transplant with any other organ.
2. Donor age: < 5 years or > 70 years
3. Patients who are recipients of A-B-O incompatible transplants

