10.8 Sample size calculation

The probable difference between the CNI-free - and the CNI-group in the GFR is estimated as $\delta = 8$ ml/min with $\sigma = 16$ ml/min. With $\alpha=.05$ (two sided significance level) and $1-\beta = 90\%$ (power), $n=86$ patients per group are required to demonstrate superior efficacy of the CNI-free regimen compared to the CNI-group in the GFR using the t-test [REDACTED]. To compensate for some uncertainty of the assumptions for sample size calculation, the calculated sample size is increased by $\approx 15\%$. Therefore, a total number of $N=200$ patients ($n=100$ per treatment group) will be randomized and treated in both treatment arms after Baseline (Month 6 post Tx).

In order to achieve the planned number of randomized patients as exactly as possible which may be hampered by the delay between inclusion (Screening – Month 3 post Tx) and randomization (Baseline - Month 6 post Tx), the rate of non-randomized patients will be determined when 150 patients will be randomized, and extrapolated to a number of 200 randomized patients. Recruitment will be stopped, when 200 patients + 120% of the extrapolated rate of non-randomized patients will be included at Screening. The further 20% of non-randomized patients are considered as a safety margin to avoid underrecruitment of randomized patients.

According to amendment 4, enrollment into this study will be terminated by 31st December 2015, by that time about 165 patients will have been recruited into this trial. Under the assumptions above, this would lead to a power of 82%. Since this sample size will contain also patients who discontinued the trial/medication early or who had other protocol deviations, the actual power will even be somewhat lower.

Under the assumptions specified in the initial protocol, the study will still have 82% power with the now reduced sample size. That means that the scientific value will not

be compromised with 82% probability. However, even if the study should just fail to reach statistical significance, it will most likely still show the presence (or absence) of a non-significant trend, which would contribute to the body of evidence for this treatment option.

11 Discussion and rationale for study design features

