### 1.1 Study design

This was a prospective, multi-center, randomized, controlled, parallel group, open label study in heart transplant recipients. Enrollment was terminated at 31st December 2015 with a protocol amendment. At that time 162 de novo heart transplant patients have been randomized to the two treatment groups at Baseline visit (Month 6 post Tx). The patients were recruited from 9 transplant centers in Germany.

During the first three months post Tx the patients may have been treated according to center standards. Latest after study inclusion (Month 3 post Tx ±2 weeks), the patients received an immunosuppressive regimen consisting of Cyclosporin A (based on C0-h level) or Tacrolimus (based on C0-h level) + Everolimus (target C0-h level: 5 – 10 ng/mL) or MPA + corticosteroids.

At Month 6 (±1 week) post transplantation (Baseline), patients whose eligibility was confirmed by additional in- and exclusion criteria were randomized and hence allocated to one of the two treatment groups in a 1:1 ratio in the following way:

A randomization list was produced under the responsibility of Novartis Biometrics Department using a validated system that automates the random assignment of treatment groups to randomization numbers in the specified 1:1 ratio (CNI group, CNI-free group). The randomization scheme was reviewed and locked after approval. According to the recommendations given in the ICH E9 Guideline “Statistical Principles for Clinical Trials” (CPMP, 1998), the used block length was specified in a separate document which was withheld from the study centers. The randomization list was kept sealed in a secure location.

At Baseline visit (Month 6 post Tx), all eligible patients were given a randomization number that assigns them to one of the treatment groups. The randomization numbers were sequentially allocated to the patients per center in the order of inclusion in the randomized treatment period.

Randomization of individual patients was performed centrally by a CRO. Allocation of a patient to one of the two treatment groups was performed in the following steps.

1. Information about patient enrollment (Screening Visit – Month 3 post Tx): Study sites informed the randomization department of the CRO about each patient inclusion via fax.

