#### Baseline:

“Baseline” in the sense of “baseline value” means all values collected at Baseline visit at month 6 or, if not available, the corresponding value collected at Screening visit.

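### The primary ANCOVA is valid but adjusts for one pre-randomization GFR; adding the scheduled Month 3 value is a low-cost gain of uncertain size

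*SAP*

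**What the plan says.** Protocol 10.5.2 and SAP 2.5.2 give the same primary model. Month 18 GFR is the outcome, treatment and center are factors, and the single covariate is "baseline GFR value at Baseline visit 2 (Month 6" post transplant).

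GFR is also needed three months earlier. Inclusion criterion 3 in protocol section 5, applied at Month 3, reads "Patients with sufficient renal function, i.e. GFR >30 and <100mL/min". Table 7-1 and the Screening visit list schedule biochemistry at Month 3. Protocol 7.6 includes creatinine, urea and albumin in that panel, and these are the laboratory inputs to the MDRD formula in SAP 5.1.2.

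The SAP uses Month 3 GFR in three places, none of them the primary model:
- SAP 2.3 describes the course of GFR over the run-in period.
- SAP 2.5.4 evaluates the primary variable between Month 3 and Month 6.
- SAP 2.1.1 defines baseline as the Month 6 value or, failing that, "the corresponding value collected at Screening visit".

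SAP 1.1 reports 162 patients randomized in 9 centers, against 200 planned.

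**The concern.** A GFR calculated from one local creatinine, urea and albumin sample carries measurement noise and short-term variation. If part of the Month 6 value is noise, a second pre-randomization reading helps to predict Month 18. The residual variance and the standard error of the treatment contrast then fall, with no new data collected. The covariate is measured before randomization, so it does not bias the randomized comparison. What is at stake is precision in a trial that stopped 38 patients short of plan.

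**Working it through.** **Inputs from the documents.** Two-sided alpha 0.05, delta 8 mL/min, sigma 16 mL/min and 86 per group for 90% power by t-test (protocol 10.8); 162 randomized and 9 centers (SAP 1.1). Assumed here: an equal split of 81 per arm and no loss of analysable patients. The documents do not say whether sigma is the raw SD or the SD after baseline adjustment, and they give no correlation between visits.

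**The plan's own figures.** The noncentral t distribution gives 86 per group, with power 90.3%, so the sample size reproduces. The same inputs give 88.5% power at 162 patients and 89.1% at 165. The 82% stated for about 165 patients in protocol 10.8 and SAP section 3 does not follow from them.

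**Formula.** Let r36, r3 and r6 be the correlations of Month 3 with Month 6, Month 3 with Month 18, and Month 6 with Month 18. The partial correlation of Month 3 with Month 18, given Month 6, is

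pr = (r3 − r6·r36) / √[(1 − r6²)(1 − r36²)].

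Adding Month 3 multiplies the residual variance by 1 − pr². The equivalent sample size is 162 / (1 − pr²).

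**Case 1: Month 6 carries all the information.** Then r3 = r6·r36, so pr = 0 and the gain is 0%. Residual degrees of freedom fall from 151 to 150, an inflation of the estimated residual variance of 151/150, under 1%. Power stays at 88.5%.

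**Case 2: equal correlation rho between all three visits.** Residual variance is 1 − rho² with one value and 1 − 2rho²/(1 + rho) with two.

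| rho | one value | two values | fall | equivalent N |
|---|---|---|---|---|
| 0.5 | 0.750 | 0.667 | 11% | 182 |
| 0.6 | 0.640 | 0.550 | 14% | 189 |
| 0.7 | 0.510 | 0.424 | 17% | 195 |

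**Case 3: mixed structures.** Suppose part of the variance is persistent, part decays over time and part is noise. Two illustrations, with the decaying part retaining 0.9 of its correlation per month:
- Shares 0.4 / 0.4 / 0.2 give r36 = 0.4 + 0.4 × 0.9³ = 0.692, r3 = 0.4 + 0.4 × 0.9¹⁵ = 0.482 and r6 = 0.4 + 0.4 × 0.9¹² = 0.513. Then pr = 0.205 and pr² = 4.2%.
- Shares 0.5 / 0.3 / 0.2 give 0.719, 0.562 and 0.585. Then pr = 0.251 and pr² = 6.3%.

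Other mixtures tried gave reductions of 4.3% to 7.3%, so about 4–7% is a fair working range. It is not a bound: correlations midway between Cases 1 and 2 give 2.8% to 5.6% for r6 = r36 of 0.5 to 0.9.

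**Power at 162 if sigma = 16 is the residual SD given Month 6** (8 df for center, 1 per covariate). The present model has 88.5%. A variance reduction of 4.3% gives 89.8% and one of 7.3% gives 90.7%. The equal-correlation cases give 91.8%, 92.7% and 93.4%.

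**Power at 162 if sigma = 16 is the raw SD.** With equal correlations of 0.5, 0.6 and 0.7, the present model already has 95.5%, 97.7% and 99.3%. Two covariates give 97.2%, 98.9% and 99.8%, a gain of 0.5 to 1.7 points.

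**Recovering the whole shortfall.** An equivalent N of 200 needs pr = √(1 − 162/200) = 0.44. Under equal correlation that means rho of nearly 0.8, since pr = rho/(1 + rho).

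**The case against.** The strongest objection is that nothing is wrong. The model is pre-specified, agrees with the protocol and adjusts for the pre-randomization value nearest the outcome. That stands in full.

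The larger gains also rest on treating Months 3 and 6 as exchangeable readings, and several features of the trial count against this. Treatment up to Month 3 follows center standards (protocol section 4). Protocol section 11 chose Month 6 because adaptation to the graft is considered stable by then. Entry restricts the Month 3 range to 30–100 mL/min, although protocol section 5 repeats those limits at Month 6. On the other side, Table 6-1 lists the same CNI target ranges for Months 1–6, which gives the two readings something in common. On balance equal correlation is the optimistic case.

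There may also be less power to recover than the early stop suggests. By the plan's own inputs it is 88.5%, and the sizing counted "patients per group are required to demonstrate superior efficacy of the CNI-free regimen compared to the CNI-group in the GFR using the t-test", with no credit for any covariate.

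A late change of primary model in an open-label trial invites questions about the motive. This limits how the change is made but does not rule it out: the SAP is dated before database lock, and its section 4 already declares changes to protocol analyses.

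Finally, a Month 3 MDRD value in every patient is a design expectation. The entry criterion names no formula, and the SAP has no rule for a missing Month 3 urea or albumin. The proposal therefore needs a missing-value rule.

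**Conclusion.** The point holds as an optional, low-cost efficiency gain. The variance reduction is 0% if Month 6 carries all the information, about 4–7% under mixed structures, and 11–17% only if all visits correlate equally at 0.5–0.7. The middle range is worth about 1–2 power points at 162 patients if sigma = 16 is the residual SD. All of these sizes rest on assumed correlations, 81 per arm and no loss of analysable patients.

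A reader might infer three stronger things that the documents do not support:
- That the primary analysis is wrong or biased. It is neither.
- That the second covariate is certain to pay, or makes up for stopping at 162. The gain can be nil, and full recovery needs a partial correlation of 0.44, for which the documents give no evidence.
- That Month 3 GFR serves only as a fallback baseline. SAP 2.3 and 2.5.4 also use it descriptively.

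**What to change.** Before database lock, and without reference to results by arm:

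1. In SAP 2.5.2, specify treatment and center as factors, with Month 6 and Month 3 MDRD GFR as two covariates.
2. Do the same for Cockcroft-Gault GFR and serum creatinine, each with its own Month 3 and Month 6 values. SAP 2.6.2 already analyses these in the same way as the primary variable.
3. State a rule for a missing pre-randomization value: single imputation blind to treatment, for example from the other value. SAP 2.1.1 already does this when Month 6 is missing; the reverse case needs adding. The two covariates are then identical in those patients, so their number should be reported.
4. Show the protocol's one-covariate model alongside, and list the change in SAP section 4.

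The cost is one more model term, one degree of freedom and a declared departure from the protocol model. If the sponsor prefers to keep the protocol model as primary, the two-covariate model should be pre-specified as a supportive analysis in SAP 2.5.4.
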